The PerQseal[®] closure device implant is designed to achieve a secure and rapid seal of the access site at conclusion of the endovascular procedure, with implant absorption within 180 days.

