9. STUDY ENDPOINTS

9.1 Primary Endpoint

Incidence of major vascular access site complications related to the PerQseal[®] closure device up to 1 month from implantation, is no worse than those associated with cut-down and sutured close.

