9.3.1 Subject withdrawal/exclusion

A patient is enrolled in the study by signing an Ethics Committee approved Informed Consent Form; if he/she meets all eligibility criteria (both pre-procedure and during the procedure) and there is intent to close the femoral artery puncture site using the PerQseal® and the PerQseal® closure device contacts the patient¹.

Patients on whom the PerQseal[®] closure device is not used due to failure to meet eligibility criteria/withdrawal of consent are considered not enrolled in the study. Patients not exposed to the PerQseal[®] closure device will not require additional post procedure, pre-discharge or post discharge follow-up assessments and will not be included in safety and performance analyses. For

¹ The PerQSeal® closure device is considered to have contacted the patient if the loading cannula of the PerQSeal® closure device is inserted into the Introducer sheath.

enrolled patients that have received exposure to the PerQseal[®] closure device, but the device was not deployed for reasons other than device failure their data will be included in safety, but not performance analyses and all post procedure, pre-discharge and post discharge follow-up assessments will be performed.

A patient may withdraw from the study at any time if he/she decides to do so. However, all data collected to the time of withdrawal will be recorded in the worksheet, with a note to indicate that the patient has withdrawn their consent to further participate in the study. No further follow-up or data will be recorded for that patient on the worksheet or eCRF. Note that routine management and standard practice of care should continue for the patient without prejudice.

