10. SAMPLE SIZE

The sample size estimate outlined below is based on primary endpoint assessment only for the PerQseal® closure device.

The primary endpoint of safety will be assessed by comparison of the proportion of PerQseal® closure device closures with device related major vascular access site complications up to 1 months (P_{safety}) against a performance goal for safety (PG_{safety}) estimated from literature to be 12.5%.

The minimum sample size to demonstrate non-inferiority of safety against the literature based non-inferiority limit of 0.17 (refer to: Section 11.6 Primary Endpoint Analysis) with a one-sided significance level of 0.025 and study power of 90% is estimated to be 68 closures (assuming a 5% major vascular access site complication rate for the PerQseal® closure device). Refer to the independent statistical report for safety sample size in the CIP Appendix F: Independent Statistical Sample Size Report for Safety for details.

A one sided confidence interval is appropriate as the study is only interested in the upper bound of the major complication rate. Each complication will be analysed as a separate event.

Completion of 75 patients is recommended, this number of patients should be sufficient to demonstrate non-inferiority whilst allowing for approximately 10% dropout rate.

For Performance, in order to claim non-inferiority against technical success rate for 'perclose' or 'preclose' technique the lower bound or a (95%) confidence interval for PerQseal® technical success rate must be shown to be greater than the performance non inferiority limit. In order to achieve this, a minimum sample size of 44 closures is required to demonstrate non-inferiority in a single sample fixed one-sided significance level of 0.025 and power of 0.90 level. The secondary performance endpoint therefore does not drive sample size. The total planned sample size remains at 75 treated subjects.

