11.10 Missing data

Historically (which includes 120 subjects and 136 closures across all Frontier studies) there have not been any device related access site complications beyond patient discharge from hospital. So it is expected that all safety data will be captured for all enrolled subjects. All subjects with available data will be used in the statistical analyses. All implanted subjects will be assessed for technical success. With regard to assessment of device related complications through 1 months, data on all subjects through the point of last follow up prior to or at 1 months will be included in the analysis. For the primary analysis, no imputation is expected to be performed for missing data. However, in the unlikely event that there is missing critical safety data Bayesian models may be utilised for sensitivity to investigate the impact of incomplete follow-up.

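### SAP 9.3.1 offers only one level of withdrawal, so an access-site complication arising after consent is withdrawn but before 1 month is not counted; the likely effect is small but favours the device

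*SAP*

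**What the plan says.** SAP 9.3.1 gives the withdrawal rule: "A patient may withdraw from the study at any time if he/she decides to do so". Data collected up to that time are recorded, "with a note to indicate that the patient has withdrawn their consent to further participate in the study". After that, "No further follow-up or data will be recorded for that patient on the worksheet or eCRF". The same paragraph adds that "routine management and standard practice of care should continue for the patient without prejudice". No lesser step is described, such as ending visits while allowing a records check or a telephone call.

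The primary endpoint in SAP 9.1 covers major complications related to the "closure device up to 1 month from implantation, is no worse than those associated with cut-down and sutured close". SAP 5.1 describes an implant "with implant absorption within 180 days", so for a patient with an implant in place, withdrawal ends observation and not exposure.

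Three other places bear on the point:

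- **SAP 11.10 (Missing data)** includes each subject's data up to the last follow-up at or before 1 month, expects no imputation in the primary analysis, and mentions Bayesian models only as an optional sensitivity analysis. It states that "it is expected that all safety data will be captured for all enrolled subjects", because no device-related access-site complication occurred after discharge in 120 earlier subjects (136 closures).
- **SAP 10 (Sample size)** recommends 75 patients, "allowing for approximately 10% dropout rate".
- **SAP 11.11 and Table 23** treat missed or incomplete follow-up as protocol deviations, separately from withdrawal.

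**The concern.** The rule does not merely leave post-withdrawal data unaddressed; it stops their recording. Treatment is one implantation, so no treatment remains to be stopped, and the only open question is what information the patient still agrees to give. Some patients who want no more study visits would accept a look at their hospital notes. The SAP has no category for them.

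The primary endpoint includes components that need not appear in the first days, such as infection needing intravenous antibiotics, new limb ischaemia and permanent nerve injury. If one of these arises after withdrawal and within 1 month, the treating hospital may know of it while the eCRF cannot hold it. Under SAP 11.10 the subject's data to last follow-up still enter the analysis. With a yes/no endpoint and no imputation, a subject with no event recorded by then would count as event-free. That can only lower the observed rate, and it cannot be repaired at the analysis stage because the data were never collected.

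**Working it through.** **Inputs from the documents.** Non-inferiority limit 0.17, assumed device rate 0.05, one-sided level 0.025, power 90%, minimum 68 closures, 75 patients with about 10% dropout (SAP 10). Exact binomial bound (SAP 11.6). No post-discharge device-related access-site complication in 120 subjects (SAP 11.10).

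**Assumptions, not in the documents.** w = number of subjects withdrawing before 1 month. f = share of those subjects' events that falls after withdrawal.

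**1. The plan's own figure.** The arcsine formula for one proportion is n = [(z₀.₉₇₅ + z₀.₉₀) / (2(arcsin√0.17 − arcsin√0.05))]² = 66.02, so 67. This is close to the stated 68 but not identical. The sponsor's sample size report (CIP Appendix F) is not in the documents, so its method cannot be confirmed. For dropout, 68 × 1.1 = 74.8, so 75. Nothing below changes either figure.

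**2. The pass mark at N = 75.** Exact (Clopper–Pearson) upper bounds, to be compared with 0.17:

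| Events | One-sided 97.5% bound | One-sided 95% bound |
|---|---|---|
| 6/75 | 0.166 (passes) | 0.152 (passes) |
| 7/75 | 0.183 (fails) | 0.168 (passes) |
| 8/75 | 0.199 (fails) | 0.184 (fails) |

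The level 0.025 in SAP 10 and in the SAP 11.6 hypothesis test allows 6 events. The one-sided 95% bound, also in SAP 11.6, allows 7. That conflict is a separate matter, so both are carried here.

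**3. Likely size.** With 0 events in 120, the one-sided 97.5% upper bound is 1 − 0.025^(1/120) = 0.030 per subject. For 7 withdrawals after discharge, 7 × 0.030 = 0.21, so at most about 0.2 expected missed events.

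**4. Upper case.** 10% of 75 is 7.5; take w = 7, all before 1 month. Recorded events are then Binomial(75 − w, p) + Binomial(w, p(1 − f)), with the denominator held at 75. Chance of passing at a true rate p = 0.17:

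| | No withdrawals | f = 0.25 | f = 0.5 | f = 1 |
|---|---|---|---|---|
| 6 or fewer events (0.025) | 2.0% | 2.5% | 3.0% | 4.3% |
| 7 or fewer events (one-sided 95% bound) | 4.6% | 5.5% | 6.5% | 9.0% |

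**5. At the planned rate.** With p = 0.05, w = 7 and a pass mark of 6 events, the chance of passing is 91.9% with no withdrawals, 92.7% at f = 0.25 and 93.4% at f = 0.5. Lost events would therefore turn a fail into a pass in about 0.8% or 1.5% of trials.

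**The case against.** The strongest reply is that ending collection when consent is withdrawn is ordinary and proper. That stands for a patient who refuses any further use of data, and the rule should stay for that case.

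A reader might infer that any withdrawal, or even a declined or missed visit, ends all recording. The documents do not support this. The rule in 9.3.1 is tied to withdrawn consent to further participation, and missed assessments are handled as deviations.

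A reader might also infer that a complication which prompts withdrawal is lost. It is not, because data up to withdrawal are recorded. The per-protocol set in SAP 11.1 also does not drop a subject for early withdrawal if the endpoint has already occurred. Only later or worsening events are at risk.

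Nor do the documents show that 7 or 8 subjects will have no data to 1 month. The 10% is dropout of unstated cause and timing in a study with 3 months of follow-up, and enrolled subjects would have procedural data in any case. It is true that one unrecorded event at the pass mark changes the result, but that holds for any threshold test.

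Finally, the protocol available is a synopsis and the consent form is not visible, so consent to a records check may already exist. That hospital records would hold a later event is inferred from continuing care. List 2 already shows last contact and reason for discontinuation.

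These points limit the size of the concern. They do not supply the missing level of withdrawal in 9.3.1, and the optional, unspecified Bayesian analysis cannot recover events that were not collected. The history of 120 subjects concerns events after discharge. It does not address withdrawal before discharge, and it may not represent patients who withdraw because of a groin problem.

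**Conclusion.** The point holds in a limited form. SAP 9.3.1 has one level of withdrawal, and it stops recording within the primary safety window. SAP 11.10 then keeps the subject without imputation, so any bias favours the device.

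The likely bias is small: about 0.2 missed events or fewer in 7 withdrawals, if the earlier post-discharge experience carries over. The upper case is a rise from 2.0% to between 2.5% and 4.3% in the chance of passing at a true rate of 0.17, at one-sided 0.025. It rests on three assumptions: all 7 dropouts withdraw before 1 month, they share the same event rate, and between a quarter and all of their events fall after withdrawal. Sample size, significance level and endpoint are not called into question here. The change is worth making because it is cheap and the information cannot be recovered later.

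**What to change.** In SAP 9.3.1 and the matching protocol text, and in the consent form if it does not already do so, separate two cases:

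- **(a) The patient stops study visits.** With the patient's consent, record vital status, access-site complications and the outcome of open device-related events through 1 and 3 months, from existing records or by telephone.
- **(b) The patient withdraws consent to further data use.** Apply the present rule, that nothing further is recorded, to this case only.

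Add the type of withdrawal to List 2, next to the reason for discontinuation.

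The cost is new wording, an ethics notification, and a records check or call for a few patients.

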9.3.2 Inclusion criteria

- i. Over 18 years of age.
- ii. Subject is willing and able to provide appropriate study-specific informed consent, follow protocol procedures, and comply with follow-up visit requirements.
- iii. Clinically indicated for an endovascular procedure using a common femoral arteriotomy created by a 12 20 F sheath.

9.3.3 Exclusion criteria

General Exclusion Criteria:

- Severe acute non-cardiac systemic disease or terminal illness with a life expectancy of less than six months.
- ii. Evidence of systemic bacterial or cutaneous infection, including groin infection.
- iii. Known bleeding diathesis, definite or potential coagulopathy, platelet count < 100,000/µl or patients on long term anticoagulants with an INR greater than 1.2 at time of procedure or known type II heparin-induced thrombocytopenia.
- iv. Severe; claudication or peripheral vascular disease (e.g. Rutherford category 3 or greater or ABI < 0.5), documented untreated iliac artery diameter stenosis > 50% or previous bypass surgery/stent placement in the common femoral artery of ipsilateral limb.
- v. Known allergy to any of the materials used in the PerQseal® (refer to Instructions for Use).
- vi. Subject has undergone a percutaneous procedure using a non-absorbable vascular closure device (excluding suture mediated) for haemostasis in the ipsilateral target leg.
- vii. Patients that have undergone a percutaneous procedure in the ipsilateral leg, within the previous 30 days.
- viii. Patients that have undergone a percutaneous procedure using an absorbable intravascular closure device for haemostasis, in the ipsilateral leg, within the previous 90 days.
- ix. Evidence of arterial diameter stenosis > 20% or anterior or circumferential calcification within 20 mm proximal or distal to target arteriotomy site based on pre-procedure CT angiography.
- x. Females who are pregnant or lactating or in fertile period not taking adequate contraceptives. A pregnancy test may be performed.
- xi. Patients that have a lower extremity amputation from the ipsilateral or contralateral limb.

Procedural Exclusion Criteria*:

- xii. Arterial access other than common femoral artery obtained for ipsilateral target leg.
- xiii. Subject has a tissue tract expected to be greater than 10 cm.
- xiv. Use of thrombolytic agents within 24 hours prior to or during the endovascular procedure which causes fibrinogen < 100 mg/dl.
- xv. Significant blood loss/transfusion (defined as requiring transfusion of 4 or more units of blood products) during index procedure or within 30 days prior to index procedure.
- xvi. Activated clotting time (ACT) > 350 seconds immediately prior to sheath removal or if ACT measurements are expected to be > 350 seconds for more than 24 hours after index procedure.
- xvii. Target puncture site is located in a vascular graft.
- xviii. Target arteriotomy in the profunda femoris or superficial femoral artery or is in common femoral artery, but within 10 mm proximal of the bifurcation of the Superficial Femoral /Profunda Femoris artery.
- xix. PerQseal[®] Introducer-sheath to ipsilateral femoral artery diameter ratio is greater than or equal to 1.05. (For S Introducer vessel lumen diameter of less than 6 mm. For L Introducer vessel lumen diameter of less than 7 mm.)
- xx. Subjects with an acute haematoma of any size, arteriovenous fistula or pseudoaneurysm at the target access site; or angiographic evidence of arterial laceration or dissection within the external iliac or femoral artery before the use of the PerQseal® closure device.

*May not be known until after the patient has given informed consent and the procedure has started. In this event, the PerQseal® should not be used and the patient should be considered excluded from the study and intention to treat analysis.

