- Failure of a closure device to achieve haemostasis at the arteriotomy site leading to alternative treatment (other than manual compression or adjunctive endovascular ballooning)

¹ Kappetein AP, Head SJ, Généreux P, et al. Updated standardized endpoint definitions for transcatheter aortic valve implantation: the Valve Academic Research Consortium-2 consensus document. European Journal of Cardio-Thoracic Surgery 42 (2012) S45–S60 (Ref. 6).

iv. BARC Bleeding Definitions (Ref. 7)

Life-threatening or disabling bleeding

- Fatal bleeding (BARC type 5) OR
- Bleeding in a critical organ, such as intracranial, intraspinal, intraocular, or pericardial necessitating pericardiocentesis, or intramuscular with compartment syndrome (BARC type 3b and 3c) OR
- Bleeding causing hypovolemic shock or severe hypotension requiring vasopressors or surgery (BARC type 3b) OR
- Overt source of bleeding with drop in haemoglobin of ≥5 g/dL or whole blood or packed red blood cells (RBCs) transfusion ≥4 units* (BARC type 3b)
 - *Given one unit of packed RBCs typically will raise haemoglobin concentration by 1 g/dL, an estimated decrease in haemoglobin will be calculated.

Major bleeding (BARC type 3a)

- Overt bleeding plus haemoglobin drop of 3.0 g/dL to ≥5 g/dL (provided haemoglobin drop is related to access site bleed); AND
- Does not meet criteria of life-threatening or disabling bleeding

Minor bleeding (BARC type 2 or 3a, depending on the severity)

- Any bleeding worthy of clinical mention (e.g. access site haematoma) that does not qualify as life-threatening, disabling, or major bleeding.
- v. Haemostasis Clinically acceptable cessation of arterial bleeding.

vi. Study Variables:

- a. Have a direct impact on claims for the device.
- b. Should be directly observable.
- c. Objectively determined measures subject to minimal bias and error.
- d. Should be directly related to biological effects of the clinical condition.

vii. Influencing Variables:

- a. Any aspect of the study that can affect the outcome or study variables.
- b. Any aspect of the study that can affect the relationship between treatment and outcome.
- viii. **Device Failure** Failure of the PerQseal® to provide percutaneous access site closure resulting in interventional (e.g. stent-graft) or surgical correction.

^{*} Adapted from VARC-21

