11. STATISTICAL METHODS

11.1 Analysis populations

All Enrolled subjects (see Section 9.3 Study Population) will be analysed on an Intent-to-Treat (ITT) basis for the Primary and Secondary Endpoint of Safety.

For avoidance of doubt: The ITT analysis population includes all enrolled subjects who undergo attempted access site closure with Vivasure PerQseal® device (i.e. PerQseal® closure device is attempted to be placed into the vasculature and contacted the patient).

All closures from Enrolled subjects will be analysed on a modified Intent-to-Treat (mITT) basis for the Secondary Endpoint of Performance, excluding enrolled subjects which met an exclusion criteria (documented by a protocol deviation).

For avoidance of doubt: The mITT analysis population includes all closures from enrolled subjects who undergo attempted access site closure with Vivasure PerQseal® device (i.e. PerQseal® closure device is attempted to be placed into the vasculature and contacted the patient), with the exception of devices that were prevented from deploying for reasons listed in the exclusion criteria or due to issues associated with the primary procedure.

A secondary analysis population for the primary safety endpoint will include Per-Protocol (PP) for Primary Safety. The PP is a subset of the ITT analysis population with no major protocol deviations and who experienced the safety endpoint or did not prematurely withdraw from the study prior to being evaluated for the primary safety endpoint.

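### The main mITT sentence in SAP 11.1 has no time limit, so exclusion xv (4 or more units transfused during the index procedure) could drop a failed closure from the technical-success analysis

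*SAP*

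**What the plan says.** **The criterion.** Procedural exclusion xv, in the same words in the protocol and SAP 9.3.3, is "Significant blood loss/transfusion (defined as requiring transfusion of 4 or more units of blood products) during index procedure", or within the 30 days before it. Two neighbouring criteria carry timing words: xvi ("Activated clotting time (ACT) > 350 seconds immediately prior to sheath removal") and xx ("before the use of the PerQseal® closure device").

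**The outcome.** SAP 4.2 iv lists "packed red blood cells (RBCs) transfusion ≥4 units* (BARC type 3b") among the criteria for life-threatening or disabling bleeding. The number of units is the same as in xv.

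**The analysis sets (SAP 11.1).**
- mITT, used for technical success, is described twice. The main sentence takes all closures from enrolled subjects, "excluding enrolled subjects which met an exclusion criteria (documented by a protocol deviation"). The clarification that follows takes out only devices prevented from deploying, for reasons in the exclusion criteria or because of problems with the primary procedure.
- PP, the secondary set for primary safety, requires no major protocol deviation. The SAP does not define major.
- ITT, used for primary safety, takes every enrolled subject with attempted closure and device contact. It has no eligibility exception.

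**Enrolment.** SAP 9.3 enrols a consented patient on contact with the device. SAP 9.3.1 adds a condition: "if he/she meets all eligibility criteria (both pre-procedure and during the procedure"). Its footnote 1 defines contact as insertion of the loading cannula into the Introducer sheath.

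**The concern.** An exclusion that the outcome can trigger is not a baseline restriction. If a PerQseal closure fails and the patient is transfused with 4 units in theatre, the event is a technical failure and may be a major complication. As worded, it also meets xv. Applying xv to that patient removes the failure from numerator and denominator together, so a device-caused event that is removed can only favour the device. The study has one arm and no blinding, so the classification could be made with the outcome known.

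The result most exposed is the technical-success comparison with the 0.81 limit. The PP safety analysis is exposed to a lesser degree.

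**Working it through.** **1. Can closure fall within the index procedure?** The term is not defined. SAP 4.2 xii runs overall procedural time to the end of all aseptic work on the groin. Protocol Table 1 places deployment time, time to haemostasis and need for alternative therapy in the peri-procedural column. SAP Table 11 has a single line for significant blood loss or transfusion during the procedure, not split at device use. A transfusion for a failed closure can therefore be read as falling inside xv.

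**2. What happens to that patient in each set?**

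| Set | Text that removes | Text that keeps |
|---|---|---|
| mITT (performance) | SAP 11.1 main sentence, no time limit | SAP 11.1 clarification; SAP 4.2 xiii denominator (every attempted deployment) |
| PP (safety) | No major deviations; SAP Table 23 counts eligibility breaches as deviations | No text classes a bleed after device use as a major deviation |
| ITT (primary safety) | SAP 9.3.1 eligibility during the procedure; SAP 9.3.3 footnote | SAP 9.3 enrolment on contact; SAP 11.1 ITT text; SAP 9.3.1 keeps exposed but undeployed patients in safety |

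**3. The plan's own figures.** The limits are 0.13 + 0.04 = 0.17 (safety, SAP 11.6) and 0.84 − 0.03 = 0.81 (performance, SAP 11.7). The safety sample size (5% against 0.17, one-sided 0.025, 90% power) under the arcsine formula is

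((1.9600 + 1.2816) / (2·asin√0.17 − 2·asin√0.05))² = (3.2415 / (0.8500 − 0.4510))² = 66.02, so 67.

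That is one below the stated 68. The sample size is not in dispute here.

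**4. Effect of one removal.** The SAP specifies exact binomial limits. For x in n they are:
- upper limit = Beta quantile at 1 − α with parameters (x + 1, n − x)
- lower limit = Beta quantile at α with parameters (x, n − x + 1)

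One event is taken out of both numerator and denominator. The performance rows assume 75 closures, one per patient.

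| Endpoint (limit) | One-sided α | All kept | One failure removed |
|---|---|---|---|
| Performance (0.81) | 0.025 | 67/75: 0.8006, fails | 67/74: 0.8148, passes |
| Performance (0.81) | 0.05 | 66/75: 0.7999, fails | 66/74: 0.8134, passes |
| Safety (0.17) | 0.025 | 7/75: 0.1829, fails | 6/74: 0.1682, passes |
| Safety (0.17) | 0.05 | 7/75: 0.1682, passes | no reversal possible |
| Safety (0.17) | 0.05 | 8/75: 0.1842, fails | 7/74: 0.1703, fails |

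The level matters because SAP 11.6 asks for a one-sided 95% bound and then tests at 0.025. The performance reversal occurs at either level. The safety reversal at 75 subjects occurs only at 0.025. With 68 subjects it occurs at both: 6/68 (0.1822) to 5/67 (0.1656) at 0.025, and 7/68 (0.1847) to 6/67 (0.1691) at 0.05.

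**5. Average effect on safety, if events were removed.** Take n = 75, a true rate of 0.17 and one-sided 0.025, and let each major event be removed with probability s. Type I error is 0.0204 at s = 0, 0.0362 at s = 10% and 0.0605 at s = 20%. The share s is an assumption; the documents give no figure.

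**The case against.** The best defence is the footnote to the procedural exclusions. It covers criteria that "May not be known until after the patient has given informed consent and the procedure has started" and goes on to say that the device should then not be used. This presupposes that the device can still be withheld, so xv would act before device use without saying so. Other text describes closure as coming after, or at the conclusion of, the main procedure. SAP 11.11 describes eligibility deviations in terms of baseline criteria, and SAP 4.2 xv defines baseline as before the intervention. SAP 4.2 xiii counts a device malfunction that leads to alternative therapy as a technical failure.

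Much of this stands, and it rules out two stronger readings that a reader might infer.

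- **That the plan removes device-caused bleeds from the primary safety analysis.** It does not say so. Removal would require reading the SAP 9.3.1 condition as retroactive un-enrolment, against enrolment on contact in SAP 9.3 and the ITT text of SAP 11.1.
- **That the worst device failures in general are removed.** Only bleeds transfused with 4 or more units during the procedure could meet xv. A bleed that qualifies as life-threatening only through fatal outcome, shock, critical-organ bleeding or haemoglobin drop does not meet it, nor does one transfused later.

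The defence does not settle mITT. The main sentence concerns subjects who are already enrolled and so already exposed, and a footnote about withholding the device does not reach them. The baseline wording in SAP 11.11 is not repeated in Table 23.

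The numerical examples are boundary cases. At the assumed 5% rate, exactly 7 events in 75 has a probability of about 5%, and one of the 7 would have to be this kind of bleed.

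**Conclusion.** The concern holds for the technical-success analysis. SAP 11.1 gives two different mITT populations, and the broader exclusion can be triggered by the outcome through xv. It holds conditionally for PP, if such a breach is classed as a major deviation. For the primary ITT safety set the passages are ambiguous, and most of them favour keeping the exposed patient.

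One reclassified closure moves the lower performance bound by about 0.014 (0.8148 − 0.8006), which is enough to reverse a result at the boundary. A safety reversal would also need removal from the set in question and, at 75 subjects, the 0.025 level.

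The conclusion assumes that the index procedure includes closure and that at least one in-theatre transfusion of 4 or more units follows device contact. The documents give no frequency for such bleeds, so the expected effect cannot be stated and may be small.

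**What to change.** 1. In SAP 11.1, state that eligibility for ITT, mITT and PP is judged only on facts arising before device contact, as footnote 1 of SAP 9.3.1 defines it, and that no later event removes a subject or closure from any analysis set.
2. Align the two mITT sentences with each other and with the technical success denominator in SAP 4.2 xiii.
3. Define a major protocol deviation for PP.
4. Reconcile exclusion xv in the protocol, SAP 9.3.3 and SAP Table 5 with SAP 9.3, SAP 9.3.1 and the footnote to the procedural exclusions, so that its timing is stated once. The content of the clinical criterion is for the sponsor.

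The cost is a few sentences, with no extra patients, data or procedures. The downside is that the observed rates may be slightly less favourable to the device.
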